**Table 18: Laboratory Data to Be Included**

Summary Type	Include central lab results?	Include local lab results?
Subject-Incidence of Treatment Emergent Laboratory Abnormalities in Selected Laboratory Tests by CTCAE Grade	Y	Y
Change from Baseline in Laboratory Values	Y	Y
Shift from Baseline in Laboratory Values by CTCAE Grade	Y	Y
Shift from Baseline in Laboratory Values by High/Low/Normal	Y	Y
Shift from Baseline in Laboratory Values by Sponsor-defined Grades	Y	Y
Laboratory Abnormalities with a subject-incidence of $\geq 5\%$ (All Grades) or $\geq 2\%$ (Grades 3-4) in either arm	Y	Y
Laboratory Abnormalities with a subject-incidence of $\geq 5\%$ (All Grades) or $\geq 2\%$ (Grades 3-4) in the experimental arm	Y	Y
Laboratory Abnormalities with an increase in subject-incidence of $\geq 5\%$ (All Grades) or $\geq 2\%$ (Grades 3-4) in the experimental arm	Y	Y

## 8.8. Vital Signs

### 8.8.1. Variables

The following vital signs will be summarized:

- Weight
- Systolic blood pressure (mmHg)
- Diastolic blood pressure (mmHg)

### 8.8.2. Analysis

Subject incidence of clinically meaningful changes since baseline for weight and blood pressure will be presented as shown below:

- Proportion of subjects with weight loss  $\geq 10\%$  after first dose
- Subjects with at least 2 post-baseline assessments and who got worse since baseline and met the following blood pressure criteria on 2 or more visits (need not be consecutive) after first dose (JNC criteria were modified to include single measurement per time point when triplicate assessments were unavailable; Chobanian et al 2003):
  - Pre-hypertension: SBP 120-139 mmHg or DBP 80-89 mmHg
  - Stage 1: SBP 140-159 mmHg or DBP 90-99 mmHg
  - Stage 2: (SBP  $\geq 160$  mmHg and DBP  $<120$  mmHg) or DBP 100-119 mmHg
  - Stage 3: DBP  $\geq 120$  mmHg

Only results with assessment dates through the end of the standard safety observation period (see [Section 4.5](#)) will be considered for the summaries.

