**Table 6-7: Management of Hypertension Associated with Cabozantinib**

Criteria for Dose Modifications	Treatment/Cabozantinib Dose Modification
> 150 mm Hg (systolic) a and < 160 mm Hg OR > 100 mm Hg (diastolic) and < 110 mm Hg	
 
Optimize antihypertensive medications by adding new or additional antihypertensive medications and/or increase dose of existing medications.
 
Reduce cabozantinib treatment by one dose level if optimal antihypertensive therapy (usually to include 3 agents) does not result in BP <150 mm Hg systolic and <100 mm Hg diastolic
 
If subject is symptomatic interrupt cabozantinib treatment
 

≥ 160 mm Hg (systolic) OR ≥ 110 mm Hg (diastolic)	
 
Reduce cabozantinib by one dose level or interrupt cabozantinib treatment per investigator discretion
 
Add new or additional anti-hypertensive medications and/or increase dose of existing medications and monitor subject closely for hypotension. If optimized antihypertensive therapy (usually to include 3 agents) does not result in BP < 150 mm Hg systolic and < 100 mm Hg diastolic, cabozantinib treatment should be dose reduced further or interrupted
 
Cabozantinib treatment should be dose interrupted if upper limits of systolic BP (≥ 160 mm Hg) are sustained and not adequately manageable or if systolic BP is > 180 mm Hg or sustained diastolic BP > 110 mm Hg, or if subject is symptomatic
 
Re-start cabozantinib treatment at the most tolerable dose and re-escalate only if BP falls to and is sustained at < 150 mm Hg systolic and < 100 mm Hg diastolic
 

Hypertensive emergency b	
 
Discontinue cabozantinib treatment
 

BP, blood pressure.

a The investigator may decide to initiate or adjust antihypertensive treatment at a lower threshold than systolic BP >150 mm Hg or diastolic BP > 100 mm Hg based on their clinical judgment and assessment of the individual subject.

b Hypertensive emergency is defined as uncontrolled elevated BP with clinical evidence of progressive or impending end-organ damage (eg, myocardial infarction/ischemia, intracranial hemorrhage, cerebral ischemia, pulmonary edema, encephalopathy, kidney damage).

CONFIDENTIAL

Protocol XL184-313 Protocol Amendment 3.0  
Page 95 of 193

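### The blood-pressure rows in SAP 8.8.2 have upper limits and no at-or-above rule, so a subject can drop out of every stage by getting worse

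*SAP*

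**What the plan says.** SAP Section 8.8.2 (Vital Signs, Analysis) defines the blood-pressure summary. It covers "Subjects with at least 2 post-baseline assessments and who got worse since baseline" who also "met the following blood pressure criteria on 2 or more visits (need not be consecutive) after first dose". Four rows follow:

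- The mildest row is bounded above on both components: "Pre-hypertension: SBP 120-139 mmHg or DBP 80-89 mmHg".
- The next row up is bounded in the same way: "Stage 1: SBP 140-159 mmHg or DBP 90-99 mmHg".
- The third row has no systolic ceiling but does have a diastolic cap: "Stage 2: (SBP $\geq 160$ mmHg and DBP $<120$ mmHg) or DBP 100-119 mmHg".
- The top row, Stage 3, looks at diastolic pressure alone, from 120 upward with no ceiling.

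The section then limits the data: "Only results with assessment dates through the end of the standard safety observation period" are used. Under SAP Section 4.5.1 that period closes no later than 30 days after the last dose of the last component.

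The section does not say whether the rows are cumulative or exclusive, whether a higher-stage visit counts toward a lower row, or what to do with a visit that meets two rows. It specifies no other blood-pressure summary, although Protocol Section 9.4.3 plans changes or shifts from baseline in vital signs.

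**The concern.** A severity table should be monotone: a subject whose readings get worse should stay in the same row or move to a higher one. With bounded rows, a two-visit requirement and no carry-down from higher stages, that property fails. One Stage 1 visit and one Stage 2 visit can leave the subject with a single visit in each row and so counted in neither.

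Hypertension is a recognised cabozantinib toxicity (Protocol Sections 6.6 and 6.6.2.1) with its own management table (Table 6-7), so the table will be read. The SAP avoids this problem elsewhere. Adverse events are shown by worst severity (Table 15), laboratory values by maximum post-baseline grade (8.7.2) and performance status by worst value (8.9). Dose holds use nested thresholds of at least 7, 14 and 21 days (6.6.2).

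**Working it through.** The documents give no figure for this table, so there is nothing to reproduce. The check is to code the four rows literally and count a row when at least two visits meet it.

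**Step 1: rows met by single visits**

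| Visit | Rows met |
|---|---|
| 150/95 | Stage 1 |
| 165/105 | Stage 2 |
| 180/122 | Stage 3 (Stage 2 is excluded by the diastolic cap) |
| 150/85 | Stage 1 by systolic, pre-hypertension by diastolic |
| 165/88 | Stage 2 by systolic, pre-hypertension by diastolic |
| 145/92 | Stage 1 |
| 165/95 | Stage 2 by systolic, Stage 1 by diastolic |
| 150/105 | Stage 1 by systolic, Stage 2 by diastolic |
| 155/122 | Stage 1 by systolic, Stage 3 by diastolic |

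**Step 2: rows met on two visits**

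| Visits | Counted in |
|---|---|
| 150/95 twice | Stage 1 |
| 150/95, 165/105 | no row |
| 165/105, 180/122 | no row |
| 150/95, 165/105, 180/122 | no row |
| 150/85, 165/88 | pre-hypertension only |
| 145/92, 165/95 | Stage 1 |
| 150/95, 150/105 | Stage 1 |
| 150/105, 155/122 | Stage 1 only |

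The first two lines show the failure: the subject is Stage 1 if the second visit repeats 150/95 and disappears if it rises to 165/105. The last three lines show the or criteria keeping a pair in the table, though below its worst visit.

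**Step 3: how often an adjacent-stage pair is lost.** Five assumed bivariate-normal distributions were used: systolic mean 135-145, SD 18-20; diastolic mean 82-90, SD 11-12; correlation 0.3-0.8. Each visit was labelled by the highest row it meets.

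- Stage 1 with Stage 2: 48-56% of pairs are in none of Stages 1-3, and 36-45% are in no row at all.
- Stage 2 with Stage 3: 80-99% are in no row. The diastolic cap on Stage 2 causes this, since Stage 2 has no systolic ceiling and Stage 3 has no ceiling.

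**Step 4: how often a subject is lost.** Simulation of 40,000 subjects per scenario. Assumptions: mean 136/82 or 128/78; between-subject SD 10 systolic and 7 diastolic; within-subject SD 12 and 8; systolic-diastolic correlation 0 to 0.7; no treatment response; worse-than-baseline condition not applied. The denominator is subjects with systolic at least 140 or diastolic at least 90 on two or more visits.

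| Visits | In no Stage 1-3 row |
|---|---|
| 2 | about 10-24% |
| 4 | about 3-8% |
| 10 or more | under 2% |

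Most subjects missing from Stages 1-3 at 4 or more visits still appear as pre-hypertension. At mean 136/82 and correlation 0.5, at most 0.2% are in no row at all.

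**Step 5: set against the schedule.** Protocol Appendix A takes vital signs after first dose at Weeks 4, 7, 10 and 14, then every 4 weeks. By Week 50 that is 4 + (50 − 14)/4 = 13 visits. A subject treated for a year has a small chance of being missed; one who stops after Week 7 may have only two or three readings.

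**The case against.** The best case against the point has four parts.

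- **The SAP does not say that both visits must fall in the same row.** That is so. Row by row is the natural reading of a criterion followed by a list, but it is an inference. The silence does not rescue the table, because literal, highest-stage-only and cumulative coding would each give a different result.
- **Under the planned schedule the loss is small.** Expected treatment averages 12-18 months (Protocol Section 3.2). From 4 visits on, at most 0.2% of simulated subjects with two or more Stage 2-or-worse visits miss both the Stage 2 and Stage 3 rows (mean 136/82, correlation 0.5). This stands, and it confines the problem to subjects with few visits.
- **Managed hypertension is captured elsewhere.** Vital signs that change management are recorded as adverse events (Protocol Sections 8.1.1 and 8.1.2) and tabulated by worst grade (SAP Table 15). This also stands.
- **The table is descriptive.** No formal safety comparison is planned.

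A reader might also infer more than the documents support:

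- *Every mixed-stage pair is counted nowhere.* Not so: 145/92 with 165/95 counts in Stage 1.
- *The overlapping rows push Stage 2 readings down to the mildest row.* Not so: 165/85 meets pre-hypertension by diastolic and still counts toward Stage 2. The overlap inflates the pre-hypertension row and removes no one from Stage 2.
- *The table understates hypertension mainly in the experimental arm.* This is not shown. The documents give no blood pressures by arm. In the simulation at correlation 0.5, the lower mean (128/78) gave a slightly higher share lost from 4 visits on: about 5% against 4% at 4 visits, and 0.8% against 0.4% at 13.
- *Treatment changes between visits often move the second reading to another row.* Protocol Table 6-7 does say "Optimize antihypertensive medications by adding new or additional antihypertensive medications and/or increase dose of existing medications", but its first level starts above 150 systolic or 100 diastolic, so much of Stage 1 triggers nothing. Section 6.6.2.1.5 requires a confirmatory measurement before a dose decision. The effect on row membership is unquantified.

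**Conclusion.** The point holds in a limited form. Coded as written, SAP 8.8.2 gives a non-monotone severity count: a subject with visits in two adjacent stages can be counted in no stage, or only in a row below the worst visit. The worked pairs establish this without any distributional assumption, given the row-by-row reading.

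The size does depend on assumptions. The ranges in Step 4 rest on assumed normal distributions, because the documents give no blood-pressure data. They support saying that the loss is concentrated in subjects with few visits, such as early discontinuers. They do not support any statement about a difference between arms. Severity is minor: a descriptive safety table, with no effect on alpha, power or any efficacy result.

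**What to change.** In SAP 8.8.2, assign each visit once, to the stage given by its worse component. Then report cumulative rows, each on two or more visits, using the SAP's own cut-points:

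- Stage 1 or higher: systolic at least 140 or diastolic at least 90.
- Stage 2 or higher: systolic at least 160 or diastolic at least 100.
- Stage 3: diastolic at least 120.

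Add one row for the worst stage at any single post-dose visit, so that subjects with few readings are represented. With these rows, every Stage 1 plus Stage 2 pair counts in Stage 1 or higher and every Stage 2 plus Stage 3 pair counts in Stage 2 or higher; none is lost.

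The cost is a few lines of SAP text and a small programming change. The rows become cumulative, so they no longer read as separate bands and the table needs a footnote saying so.

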## 8.9. Karnofsky/ECOG performance status

The Karnofsky/ECOG performance status of the subject will be assessed during screening and at each scheduled safety assessment starting on W1D1 (see [Appendix F](#) for KPS/ECOG-PS criteria). For the purpose of evaluating safety, Karnofsky/ECOG will be summarized as shift from baseline tables for, at minimum, the worst value recorded after the initiation of study treatment. Only results with assessment dates through the end of the standard safety observation period (see [Section 4.5](#)) will be tabulated in summary tables.

Frequencies of ECOG worsening of  $\geq +1$  and  $+2$  change from baseline to worst value after first dose will also be summarized.

## **8.10.      Electrocardiogram (ECG)**

Only results with assessment dates through the end of the standard safety observation period (see [Section 4.5](#)) will be considered for summaries. The following categorical summaries will be presented per Investigator and per independent review:

- Number of subjects with triplicate average QTc > 500 ms or increase in triplicate average QTc from baseline of > 60 ms after first dose
  - Number of subjects with triplicate average QTc > 500 ms after first dose
    - Number of cases referred for independent review
    - Number of cases confirmed as QTc > 500 ms by independent review
  - Number of subjects with increase in triplicate average QTc from baseline of > 60 ms after first dose
- Number of subjects with increase in triplicate average QTc from baseline of > 30 ms after first dose

For the above summaries, the most-recent average value from triplicate measurements taken before first dose will be used as baseline. If no triplicate measurements were taken before first dose, the most-recent single or duplicate value taken before first dose will be used as baseline. If > 3 measurements are taken for an assessment, all will be included in the average.

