## **5.7.4 Electrocardiograms**

At screening and during the study, single ECG assessments will be performed with standard 12-lead ECG equipment according to standard procedures to determine the corrected QT interval calculated by the Fridericia formula (QTcF). A QTcF  $\leq$  500 ms per ECG within 14 days before randomization is required to demonstrate eligibility for study treatment. If at any time a single ECG shows a QTcF with an absolute value  $>$  500 ms or an increase in the QTcF of at least 60 ms from baseline, two additional ECGs at intervals of approximately 3 min must be performed within 30 min after the initial ECG, and the average of these three consecutive results for QTcF will be used as the value assessed (see [Section 6.6.2.1.15](#)).

ECGs will be performed at the time points indicated in [Appendix A](#).

Abnormalities in the ECG that lead to a change in subject management (eg, dose reduced or interrupted, treatment discontinued, requirement for additional medication or monitoring) or result in clinical signs and symptoms are considered clinically significant for the purposes of this

study and will be deemed AEs. If values meet criteria defining them as serious, they must be reported as SAEs ([Section 8.2](#)).

The Fridericia formula is depicted below for calculation of the QTcF value.

$$QTcF = \frac{QT}{RR^{1/3}}$$

QT = measured QT interval in milliseconds; RR = measured R to R interval (which can be derived from the heart rate as 60/heart rate)

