#### **6.6.2.1.15 Corrected QT Prolongation**

The effect of orally administered cabozantinib 140 mg qd on QTc interval was evaluated in a placebo-controlled study in subjects with MTC. A mean increase in QTcF of 10-15 ms was observed after 4 weeks after initiating cabozantinib treatment. A concentration-QTc relationship could not be definitively established. Changes in cardiac wave form morphology or new rhythms were not observed. No cabozantinib-treated subjects in this study had a QTcF > 500 ms. Review of the larger safety database (~5000 subjects exposed to cabozantinib in clinical trials and in post-marketing experience) confirmed the absence of safety concerns associated with QT prolongation. There were no events of torsades de pointes reported.

Concomitant treatment with strong cytochrome P450 (CYP) 3A4 inhibitors, which may increase cabozantinib plasma concentrations, should be avoided.

If at any time on study there is an increase in QTcF to an absolute value > 500 ms or an increase of > 60 ms above baseline per the site's ECG read, two additional ECGs must be performed with intervals not less than 3 min apart within 30 min after the initial ECG.

If the average QTcF from the three ECGs is > 500 ms or the average increase is > 60 ms above baseline, the following actions must be taken:

- Interrupt cabozantinib treatment
- Immediately notify the Sponsor
- Hospitalize symptomatic subjects (eg, with palpitations, dizziness, syncope, orthostatic hypotension), or those with a significant ventricular arrhythmia on ECG for a thorough cardiology evaluation and management
- Consider cardiology consultation for asymptomatic subjects for evaluation and management
- Check electrolytes, especially magnesium, potassium and calcium; correct abnormalities as clinically indicated
- Check concomitant medications for any medication that may have contributed to QT prolongation, and if possible, discontinue these medications (<http://www.qtdrugs.org>)
- Send ECGs to central ECG laboratory for independent read
- Repeat ECG triplicates hourly until the average QTcF is  $\leq$  500 ms and the average increase is  $\leq$  60 ms above baseline, or a consulting cardiologist or appropriate expert determines that the frequency of ECGs may revert to the schedule in the protocol.

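### The > 30 ms QTc row in SAP 8.10 can count only subjects who first met the > 500 ms or roughly 60 ms repeat trigger, so it undercounts moderate prolongation

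*SAP*

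**What the plan says.** SAP Section 8.10 lists the planned QTc output. It consists of categorical counts, each to be produced per Investigator and per independent review. The high-threshold row is "Number of subjects with triplicate average QTc > 500 ms or increase in triplicate average QTc from baseline of > 60 ms after first dose". The moderate row is "Number of subjects with increase in triplicate average QTc from baseline of > 30 ms after first dose". Both are defined on a triplicate average. For subjects with no triplicate before treatment the SAP provides a substitute: "the most-recent single or duplicate value taken before first dose will be used as baseline". It gives no substitute for post-dose time points.

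Protocol Section 5.7.4 says that, at screening and on study, "single ECG assessments will be performed with standard 12-lead ECG equipment". Replicates are conditional. They follow a single QTcF above 500 ms or "an increase in the QTcF of at least 60 ms from baseline, two additional ECGs", and the three results are then averaged. Section 6.6.2.1.15 words the trigger as "an increase in QTcF to an absolute value > 500 ms or an increase of > 60 ms above baseline". If the average confirms the finding, that section lists further actions, among them "Repeat ECG triplicates hourly until the average QTcF is" back within limits and "Send ECGs to central ECG laboratory for independent read". The ECG line in Appendix A does not ask for triplicates at any visit.

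Protocol Section 9.4.3 commits to summarising QTc changes or shifts from baseline by treatment group.

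**The concern.** The row's threshold (30 ms) lies below the threshold at which the measurement it needs is taken (about 60 ms, or 500 ms absolute). Scheduled ECGs, which are most of the ECG data, cannot enter the row. A low count could be read as absence of moderate prolongation when it partly reflects absence of eligible measurements.

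The blinded, placebo-controlled comparison is a good place to see a moderate shift between arms. Section 8.10 is the only part of the SAP with QTc output, and every row in it uses triplicate averages. The SAP therefore does not deliver, from the scheduled readings, the QTc change summary promised in Protocol Section 9.4.3.

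**Working it through.** The plan states no expected count, standard deviation or trigger rate for QTc, so there is no figure to reproduce. The structural point comes from reading the two rules together. The size is an illustration.

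**Who can enter the > 30 ms row**

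| Post-dose course (protocol followed) | Triplicate taken? | In the > 30 ms row? |
|---|---|---|
| Single readings rise 31 to 59 ms, QTcF at or below 500 ms | No | No, by construction |
| A single reading meets the trigger, average rise falls back to between 30 and 60 ms | Yes | Yes |
| A single reading meets the trigger, average rise stays above 60 ms | Yes | Yes, and in the > 60 ms row |

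Other possible sources of triplicates do not change this:

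- The hourly repeats in Section 6.6.2.1.15 follow only a confirmed triggered triplicate.
- Screening triplicates (exclusion criterion 8) follow only a single QTcF above 500 ms, and they are pre-dose.
- Under Protocol Section 16.4, additional assessments outside AE follow-up stay off the CRF unless specifically requested.
- The independent-review version is narrower still, because ECGs go to the central reader only after confirmation.

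**Illustration of size (all inputs assumed)**

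- Mean change μ: 0, 5, 10 or 15 ms.
- Between-subject SD: 8 or 12 ms.
- Visit SD and replicate SD: 6 and 6 ms, or 8 and 10 ms.
- Baseline QTcF: 420 ms, SD 18 ms.
- Post-dose ECG visits: 3 or 6.
- This gives 4 × 2 × 2 × 2 = 32 scenarios, with 200,000 simulated subjects each.

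Notation: b is the subject effect, v the visit error, r1 to r3 the replicate errors, and e0 the error in the baseline reading.

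- Single-reading change: D = μ + b + v + r1 − e0.
- Triplicate-average change: A = μ + b + v + mean(r1, r2, r3) − e0.
- Triggered visit: D ≥ 60, or absolute first reading > 500.
- SAP row: any triggered visit with A > 30. Comparator: any visit with D > 30.

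| μ; between-subject SD; visit/replicate SD; visits | Single reading > 30 ms (of 420) | Triggered | SAP > 30 ms row (of 420) | SAP > 60 ms row | Captured |
|---|---|---|---|---|---|
| 0; 8; 6/6; 3 | 4.4% (18) | 0.03% | 0.01% (0.0) | 0.00% | 0.3% |
| 0; 8; 8/10; 3 | 14.3% (60) | 0.43% | 0.38% (1.6) | 0.08% | 2.7% |
| 10; 8; 8/10; 3 | 30.3% (127) | 1.82% | 1.66% (7.0) | 0.54% | 5.5% |
| 15; 8; 8/10; 6 | 52.6% (221) | 5.63% | 5.31% (22.3) | 1.87% | 10.1% |
| 15; 12; 8/10; 6 | 52.4% (220) | 8.10% | 7.73% (32.5) | 3.28% | 14.7% |

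The first and last lines are the extremes of capture across the 32 scenarios. The share missed runs from 100 − 14.7 = 85.3% to 100 − 0.3 = 99.7%.

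Two cautions apply. Even with μ = 0, between 4.4% and 23.8% of subjects exceed 30 ms on some single reading, so missed does not mean missed true prolongation. Also, the > 30 ms row is not a count-for-count copy of the > 60 ms row (7.73% against 3.28% in the last line). What they share is the triggered pool.

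**The case against.** This is one descriptive safety row. No formal safety comparison is planned, and efficacy, alpha and power are untouched. Averages also protect against noise. The > 500 ms and > 60 ms rows match the protocol's trigger and its averaged-value decision rule. ECG abnormalities that change management or cause symptoms are AEs and appear in the AE tables. All of that stands. It limits the importance of the point but does not let a subject with a 31 to 59 ms rise enter the row.

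A reader might infer several stronger things that the documents do not support:

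- **The row will be almost empty, or will miss more than 90% of cases.** No trigger rate is given. In the illustration the row holds up to 7.73% of an arm, and 4 of the 32 scenarios miss less than 90%. Per-reading tail areas would also use the wrong unit, because the row counts subjects over repeated visits.
- **It is the trial's only planned view of moderate QTc change.** Protocol Section 9.4.3 still commits to a summary of QTc changes. The gap is that SAP Section 8.10 does not implement it from scheduled readings.
- **A mean rise of 10-15 ms should be expected here.** Section 6.6.2.1.15 reports that figure at 140 mg qd in a different cancer, against 40 mg here, and the protocol says its capsule and tablet formulations are not interchangeable. The same section reports no QTcF above 500 ms among cabozantinib-treated subjects in that study, and no QT safety concern in a review of about 5000 subjects.
- **All the QTc rows are defective.** The high-threshold rows are little affected.

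**Conclusion.** The > 30 ms row is wrong as defined. If the protocol is followed, it can contain only subjects who met the repeat trigger, and it excludes any subject whose rise stays at 31 to 59 ms with QTcF at or below 500 ms. That follows from the two texts and needs no assumption. The row therefore undercounts moderate prolongation and largely re-examines the subjects behind the > 60 ms row.

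The size is assumption-dependent: about 85% to over 99% of subjects with a single-reading rise above 30 ms in the scenarios shown, some of whom would be noise.

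The omission looks like an oversight. The SAP already accepts single values for baseline QTc, and Section 8.8.2 does so for blood pressure when triplicates are unavailable. The change should be made, but it concerns a safety table and no primary or secondary inference.

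**What to change.** In SAP Section 8.10:

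1. For the > 30 ms row per Investigator, define the post-dose value at each time point as the triplicate average when replicates were taken, otherwise the single or duplicate QTcF. Name QTcF as the correction.
2. Show the triplicate-only count as a separate line, so that averaged and single-reading results are not mixed.
3. Keep the > 500 ms and > 60 ms rows on the triplicate average.
4. State that the independent-review version covers only ECGs sent for central read. A single-reading fallback cannot fill it.
5. Add a by-arm summary of QTcF change from baseline at scheduled ECGs, to meet Protocol Section 9.4.3.

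Separately, Protocol Sections 5.7.4 and 6.6.2.1.15 differ on whether a rise of exactly 60 ms triggers repeats. They should be reconciled, though this does not alter the point.

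The core change is one sentence and one extra table line, using readings the protocol already schedules. The cost is noise, because the worst of several single readings will put some subjects above 30 ms in both arms. The row should therefore be read as a between-arm contrast. With between-subject SD 8, visit/replicate SD 8/10 and 3 visits, mean changes of 0 and 10 ms give 60 and 127 of 420 on single readings, against 1.6 and 7.0 under the present definition.
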